3.2.2. Secondary Efficacy Endpoints

Secondary efficacy endpoints of this study are:

- Change and percent change from baseline in plasma or serum biomarkers: 17-OHP, ACTH, androstenedione (A4), and testosterone.

3.2.3. Exploratory Efficacy Endpoints

The exploratory efficacy endpoints of this study are:

- Changes in QoL as measured using the Short Form 36(SF-36),
- Changes in Patient Global Impression of Change (PGIC),
- Changes in bother score
- Changes in CAH signs and symptoms total score,
- Changes in fasting glucose,
- Changes in hemoglobin A1c (HbA1c),
- Changes in lipid profile,
- Changes in body weight (BW) and body mass index (BMI),
- Changes in acne,
- Changes in hirsutism in females subjects,
- Changes in menstrual cyclicity in female subjects,
- Changes in TARTs and on semen analysis in male subjects.

4. STUDY DESIGN

4.1. Summary of Study Design

[figure not shown]
This is a Phase 2 study of SPR001 for the treatment of classic CAH that will provide 12 weeks of open-label treatment to eligible subjects. To be eligible for this study, an individual must either have completed Study SPR001-201 or meet criteria for SPR001-naïve subjects outlined under Eligibility Criteria.

Subjects who enroll in this study will be treated with SPR001 at 400 mg once a day (QD) during the treatment period.

Study visits will occur every 2 weeks and should be scheduled for the morning, to accommodate 8 am laboratory assessments. Study visits for screening and at Day 1 (Baseline), Week 4, Week 8, and Week 12 (end of treatment) will be conducted as in-clinic visits. Study visits at Week 2, Week 6, and Week 10 may be conducted as either in-clinic visits or in-home visits by qualified study personnel. A final safety follow-up outpatient clinic visit will occur 30 days after the last dose of study drug.

To reduce subject burden, the final safety follow-up visit in Study SPR001-201 for subjects completing that study and rolling over into this study may coincide with the screening visit of this study (with any overlapping assessments conducted only once). Subjects who completed the final follow-up visit in Study SPR001-201 >3 months before screening in this study and subjects naïve to SPR001 must complete anew all specified screening assessments for this study. Subjects will maintain a stable dose and regimen of glucocorticoids throughout this study.

Figure 1: Study Schema

4.2. Definition of Study Drugs

Study drug comprises the following:

- SPR001 400 mg once daily (two 200 mg capsules): Taken orally for up to 12 weeks in the evening (approximately 10 pm or bedtime) with a snack

4.3. Sample Size Considerations

The sample size of up to approximately 24 subjects in this study is based on an estimate of the number of subjects who may enroll either after completing Study SPR001-201 or as SPR001-naïve subjects. There is no statistical basis for the sample size,

The final sample size for the study is n=11.

4.4. Randomization

This is an open label study. All enrolled subjects receive the same treatment with no randomization.

4.5. Clinical Assessments

VISIT NUMBER	Screening Period		Treatment Period							Follow-up/ET
	¹ Screening	² Baseline	3	4	5	6	7	8		
STUDY WEEK		0	2	4	6	8	10	12	16	
STUDY DAY ²	≤30 days before Day 1	1	15	29	43	57	71	85		Last dose +30 days
Site Visits ³	X	X		X		X		X		X
Home Visits ⁴			X		X		X			
Informed consent	X									
Inclusion/exclusion criteria	X	X								
Demography ⁵	X									
Medical history ⁶	X									
Prior medications ⁶	X									
Concomitant medications ⁷	X	X	X	X	X	X	X	X	X	

¹ For subjects rolling over from Study SPR001-201, the final safety follow-up visit of Study SPR001-201 may coincide with the screening visit of this study (with any overlapping assessments conducted only once). If a subject completed the final follow-up visit of Study SPR001-201 ≤3 months before the screening period of this study, overlapping assessments conducted at that final follow-up visit need not be repeated at screening for this study. If a subject completed the final follow-up visit of Study SPR001-201 >3 months before the screening period of this study, all screening assessments must be conducted anew, including some additional screening assessments specified for such subjects.

² All visits should be performed on the indicated study days. In cases where this is not possible, the following visit windows apply: ±3 days for Visits 3 to 8 and ±7 days for the safety follow-up visit (Visit 9). All visits, including the early termination visit, should be scheduled for the morning, to accommodate 8am laboratory assessments.

³ Study visits for screening; at Weeks 0, 4, 8, and 12; and at final follow-up must be conducted as in-clinic outpatient visits.

⁴ Study visits at Weeks 2, 6, and 10 may be conducted as either in-clinic outpatient visits or in-home visits by qualified study personnel.

⁵ Demographic information needs to be collected only for SPR001-naïve subjects.

⁶ Full medical history and prior medications from the past year will be collected for SPR001-naïve subjects. If a subject completed the final follow-up visit in Study SPR001-201 before the screening period for this study, any significant medical history and medications taken during the intervening period should be captured.

⁷ Subjects should be on a stable regimen of glucocorticoid replacement for a minimum of 30 days before baseline and throughout the treatment period. On the mornings of all study visits, including screening, subjects should hold off on taking any morning glucocorticoid medication until after laboratory assessments have been completed. On all other days during the study, subjects may take any morning dose of glucocorticoid medication at their usual time.

VISIT NUMBER	Screening Period		Treatment Period							Follow-up/ET
	1 ¹ Screening	2 Baseline	3	4	5	6	7	8	9	
STUDY WEEK		0	2	4	6	8	10	12	16	
STUDY DAY ²	≤30 days before Day 1	1	15	29	43	57	71	85		Last dose +30 days
Site Visits ³	X	X		X		X		X		X
Home Visits ⁴			X		X		X			
Clinical laboratory ^{8,9}	X	X	X	X	X	X	X	X		X
HbA1c ⁸			X		X		X			X
Key hormones ^{8,10}	X	X	X	X	X	X	X	X		X
Exploratory adrenal hormones ^{8,11}			X		X		X			X
PK ^{8,12}	X	X		X		X		X		X
Hepatitis B & C and HIV screening ¹³	X									
eGFR for screening ^{13,14}	X									
Pregnancy test for WOCP ¹⁵	X	X		X		X		X		X
Vital signs ¹⁶ and body weight	X	X	X	X	X	X	X	X		X

⁸ Samples for these lab assessments will be obtained at the beginning of each study visit (8am), after overnight fast (nothing to eat since the previous midnight), and before the subject has taken any morning dose of glucocorticoid medication. If a morning dose of study drug is added, samples for these lab assessments will be obtained before the morning dose of study drug for that day (where applicable).

⁹ Clinical laboratory assessments include hematology, clinical chemistry, fasting glucose, lipid panel, thyroid panel, urinalysis, LH, FSH, inhibin B, SHBG, renin, aldosterone, and, for females only, estradiol, prolactin, and progesterone.

¹⁰ ACTH, 17-OHP, androstenedione, testosterone, and background glucocorticoid levels (cortisol/prednisolone/dexamethasone, depending on what the subject is taking) will be measured from blood samples. 17-OHP will also be measured from a saliva sample.

¹¹ A single blood sample will be drawn for measurement of exploratory adrenal hormones at each specified visit.

¹² A single blood sample will be drawn for PK measurement at each specified visit. The PK blood sample does not need to be obtained from SPR001-naïve subjects at screening.

¹³ These screening assessments will be performed for SPR001-naïve subjects and for subjects who completed the final follow-up visit in Study SPR001-201 >3 months before the screening visit for this study.

¹⁴ eGFR for screening will be calculated from blood creatinine measured as part of clinical chemistry during screening.

¹⁵ A serum pregnancy test will be performed at screening for WOCP who are SPR001-naïve and for WOCP who completed the final follow-up visit in Study SPR001-201 >3 months before the screening visit for this study. All other pregnancy tests will be urine pregnancy tests.

¹⁶ Systolic and diastolic blood pressure, pulse rate, body temperature, and respiration rate.

VISIT NUMBER	Screening Period		Treatment Period							Follow-up/ET
	1 ¹ Screening	2 Baseline	3	4	5	6	7	8		
STUDY WEEK		0	2	4	6	8	10	12	16	
STUDY DAY ²	≤30 days before Day 1	1	15	29	43	57	71	85		Last dose +30 days
Site Visits ³	X	X		X		X		X		X
Home Visits ⁴			X		X		X			
Physical examination ¹⁷	X	X		X		X		X		X
Scrotal ultrasound for males	X ¹⁸	X								X
Optional semen sample for males ¹⁹		X								X
12-lead ECG	X	X		X		X		X		X
MINI Version 7.0.2 ¹³	X									
C-SSRS	X	X		X		X		X		X
HADS	X	X		X		X		X		X
SF-36 ²⁰		X		X		X		X		X
PGIC				X		X		X		X
Bother score		X		X		X		X		
CAH signs and symptoms interview		X		X		X		X		X
Diary	X									
Dispense study drug ²¹		X		X		X				
Study drug accountability			X	X	X	X	X	X		
Review adverse events		X	X	X	X	X	X	X		X

¹⁷ A full physical examination will be conducted at baseline (Day 1) and end of treatment (Week 12) for all subjects. A full physical examination will also be conducted at screening for SPR001-naïve subjects and subjects who completed the final follow-up visit in Study SPR001-201 >3 months before the screening visit for this study. The full physical examination may exclude rectal, genitourinary, and breast exams. An abbreviated physical examination will be conducted at Weeks 4 and 8 and final follow-up. Height needs to be collected at screening only. As part of the examination of the skin, acne will be evaluated for all subjects using an IGA score at baseline and Weeks 4, 8, and 12; hirsutism will be evaluated for female subjects using an mFG score at baseline and Week 12. Female subjects will be asked about their last menstrual period as part of both full and abbreviated physical exams.

¹⁸ A scrotal ultrasound is required at screening only for SPR001-naïve male subjects.

¹⁹ All male subjects should be encouraged (though not required) to provide a semen sample. Semen will be collected from male subjects for analysis of sperm count, morphology, and motility.

²⁰ The 4-week SF-36 will be administered.

²¹ Subjects will be dispensed a 4-week supply of study drug each time. If a morning dose of study drug is added, subjects should hold off on taking their morning dose of study drug on the mornings of all study visits until after laboratory assessments have been completed. On all other days during the study, subjects should take their morning dose of study drug (if applicable) at the usual time.

5. PLANNED ANALYSES

5.1.1. Changes to Protocol Specified Analyses

Due to the low enrollment numbers for subjects enriched with acne and hirsutism at baseline (n=2), these endpoints will not be summarized.

Due to no samples collected, analysis of semen will not be summarized.

Due to the study short duration and lack of adequate baseline data, menstrual cyclicity will not be summarized.

5.1.3. Interim Analyses

As this study is open-label, data cuts may be taken during study conduct to inform the future development plan for tildacerfont. No formal statistical analyses are conducted in this SAP.

5.1.4. Final Analysis

The final analysis is planned once all enrolled subjects complete the Week 16 visit or discontinue prior to Week 16.

6. CONSIDERATIONS FOR DATA ANALYSES AND HANDLING

All data from scheduled and unscheduled visits will be presented in the subject listings.

However, unless noted otherwise, only data from scheduled/windowed visits will be included in the summaries, statistical analysis, and calculation of derived parameters.

6.1. Summary Table and Individual Subject Data Listing Considerations

Summary tables and listings (e.g., post text tables and individual subject data listings are prepared according to ICH Guideline E3) include a “footer” providing explanatory notes.

6.2. Data Management

Analyses and tabulations will generally be prepared using SAS®, version 9.3 or later.

Adverse Events

Recorded adverse events will be mapped according to the MedDRA thesaurus with Theravance review and approval of the mappings. MedDRA, version 21.0 will be used

Medications

Recorded prior and concomitant medication names will be mapped according to the World Health Organization Drug Dictionary (WHODD) for this study with Theravance review and approval of the mappings. The 3Q2108 version of the WHODD will be used.

Medical History

Medical history will be mapped according to MedDRA version 21.0 and will be provided in listings.

6.3. Data Presentation Conventions

Table, Figure and Listing titles

Table, figures and listing titles are denoted in underlined text in this SAP. For a complete list, see Appendix Section 11.3.

Reporting Formats

Appendix Section 11.1 lists the available reporting formats for summaries.

Presenting Multiple Summaries on Same Table Summary

In summary tables in which multiple single line frequency summaries are being presented, the “n line” can be suppressed in the individual summaries and presented at the top of the summary a single time.

Ordering of Treatment Headers in Summary Tables

In summary tables, treatment headers will be presented in the following order:

- Tildacerfont 400 mg QD.

Rounding

In general, the convention for rounding percentages is as follows:

- Values greater than or equal to x.x5 are rounded up,
- Values between 0 and less than x.x5 are rounded down,
- Values between -x.x5 and 0 are rounded up,
- Values less than or equal to -x.x5 are rounded down.

Significant Digits

Raw measurements will be reported the same as the data captured electronically or on the CRFs. Exceptions will be made for values reported with greater than 4 significant digits (round to 4 significant digits using a similar criterion as for percentages with the 5 in the last digit)).

The following significant digit convention will be used for the purposes of summarizing data in tables:

- Mean, median: 2 significant digits,
- Standard deviation: 3 significant digits,
- Minimum, maximum: 2 significant digits,
- Percentages: 1 decimal place.

P-values

P-values will be reported with 4 significant digits except when reporting p-values less than 0.001, reported as < 0.001. No p-values smaller than <0.001 will be reported.

Colors/Symbols in Figures

In figures that only contain the 3 treatment groups, the following colors will be used:

- SPR001 400 mg QD (dodger blue- CX1E90FF / Square filled),

6.4. Analysis Populations

6.4.1. Screen Failures

Subjects who give informed written consent but are not randomized are considered screen failures. Screen failure subjects and the main reason for screen fail will be captured in the EDC.

6.4.2. Enrolled Population

The Enrolled analysis set will include all subjects who were enrolled into the study.

6.4.3. Safety Population

The Safety analysis set will include all subjects who

1. Were enrolled into the study, and,
2. Received at least one dose of study drug.

The Safety analysis set is the primary analysis set for all analyses.

6.4.4. Per-Protocol (PP) Population

The Per-protocol analysis set included all subjects in the safety analysis set who meet the following criteria:

1. No major analysis protocol deviations

Treatment assignment will be based on actual treatment.

Major Analysis Protocol Deviations

Major analysis protocol deviations that could potentially affect the conclusions of the study will be identified prior to database lock. Major analysis protocol deviations include:

1. Study drug compliance defined as compliance $< 80\%$ or $\geq 120\%$ over the interval from first to last dose for the treatment period,

Subjects with major analysis protocol deviations will be identified before the database lock.

6.4.5. Examination of Subgroups

The following subgroups are pre-defined:

1. Sex: [a] male, [b] female
2. Baseline hormone control: [a] severe/moderate control issues, [b] mild control issues
3. Baseline Glucocorticoid category: [a] Non-Dexamethasone [b] Dexamethasone

Selected analysis will be conducted using the subgroup analysis sets.

6.5. Baseline Definition

The following table indicates the baseline to be used in the analysis.

Table 2: Baseline Specifications for Specific Variables

Parameter	Day 1 pre-dose
Laboratory (Chemistry, Hematology, Urinalysis)	x
Biomarkers	x
ECG	x
Vital signs	x
PROs	x

6.6. Derived and Transformed Data

6.6.1. General Variable Definitions

Baseline Age

Subject's age in years will be calculated based on date of informed consent date using the following formula:

Age (year) = FLOOR ((date of informed consent – date of birth)/365.25*12) where FLOOR () function returns the integer part of the result.

Study Day

If the date of interest occurs on or after the first dose date, then study day will be calculated as (date of interest – date of first dose) + 1.

If the date of interest occurs prior to the first dose date, then study day will be calculated as (date of interest – date of first dose).

There is no study day 0.

BMI

BMI will be calculated and converted to metric units by the following:

$$BMI \left(\text{kg} / \text{m}^2 \right) = \frac{weight(\text{kg})}{height(\text{m})^2}.$$

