#### *Inclusion Criteria for All SPR001-Naïve Subjects*

- Male and female subjects ≥18 years old
- Has a documented historical diagnosis of classic CAH due to 21-hydroxylase deficiency based on documented genetic mutation or elevated 17-OHP
- Known or suspected differential diagnosis of any of the other known forms of CAH, including non-classic CAH, requires Medical Monitor approval for enrollment

- Has serum 17-OHP  $\geq 800$  ng/dL at screening. On the day of screening, the subject should take any morning glucocorticoid medication after the screening blood draw to allow for an unimpeded assessment of 17-OHP.
- Is on a stable regimen of glucocorticoid replacement for  $\geq 12$  weeks before baseline that is expected to remain stable throughout the study
- Agrees to follow contraception guidelines ([Section 5.3.5](#)). Male subjects must also agree to refrain from donating sperm throughout the treatment period and for 90 days after the last dose of study drug.
- Is able to understand all study procedures and risks involved and provides written informed consent indicating willingness to comply with all aspects of the protocol

*Additional Inclusion Criteria for Enriched Population of SPR001-Naïve Subjects*

- If male, must be 18 to 35 years old, inclusive.
- If male, must have a diagnosis of TART(s) confirmed via scrotal ultrasound at screening with at least 1 lesion having a diameter  $\geq 4$  mm
- If female, must have at least one of the following clinically significant sequelae of androgen excess:
  - Clinically significant acne defined as an Investigator's Global Assessment (IGA) score  $\geq 2$  at screening
  - Clinically significant hirsutism defined as a modified Ferriman-Gallwey (mFG) score  $\geq 6$  at screening
  - Verifiable history (based on medical records or ability to obtain an accurate history from the individual) of ovulatory dysfunction defined as having at least 1 year of menstrual cycles that last  $\geq 45$  days or having  $\leq 8$  menstrual periods within the past year, if the subject is not on a hormonal contraceptive

*Exclusion Criteria for All SPR001-Naïve Subjects*

- Has had a clinically significant unstable medical condition, medically significant illness, or chronic disease within 30 days of screening, including but not limited to:
  - A malignancy or  $<3$  years of remission history from any malignancy, other than successfully treated localized skin cancer

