### **5.2.2 Additional Inclusion Criteria for Enriched Population of SPR001-Naïve Subjects**

After an initial enrollment of at least 3 SPR001-naïve subjects who must fulfill only the inclusion criteria in [Section 5.2.1](#), the Sponsor may decide to require all SPR001-naïve subjects who enroll subsequently to satisfy all of the following additional inclusion criteria for an enriched population of SPR001-naïve subjects:

1. If male, must be 18 to 35 years old, inclusive.
2. If male, must have a diagnosis of TART(s) confirmed via scrotal ultrasound at screening with at least 1 lesion having a diameter  $\geq 4$  mm
3. If female, must have at least one of the following clinically significant sequelae of androgen excess:
  - a. Clinically significant acne defined as an IGA score  $\geq 2$  at screening
  - b. Clinically significant hirsutism defined as an mFG score  $\geq 6$  at screening
  - c. Verifiable history (based on medical records or ability to obtain an accurate history from the individual) of ovulatory dysfunction defined as having at least 1 year of menstrual cycles that last  $\geq 45$  days or having  $\leq 8$  menstrual periods within the past year, if the subject is not on a hormonal contraceptive

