7.4. Demographic and Baseline Characteristics

Demographics and baseline characteristics will be summarized.

Label	Reporting Format
Subject Age	C
Sex	MF; Male, Female, Missing
Ethnicity	MF; Hispanic or Latino, Not Hispanic or Latino, Not Reported, Unknown, Missing
Race	MF; White, Black or African American, Asian, American Indian or Alaska Native, Native Hawaiian or Other Pacific Islander, Other, Multiple Race, Missing
Baseline Weight (kg)	C
Baseline Height (cm)	C
BMI (kg/m ²)	C

A listing will also be provided.

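### The SAP's formula for age in years returns completed months, which would misstate age in the demographics table and listing if programmed as written

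*SAP*

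**What the plan says.** SAP 6.6.1 (Baseline Age) states that a subject's "age in years will be calculated based on date of informed consent date using the following formula". The formula labels its result as a year value, takes the consent date minus the birth date, and ends with "date of birth)/365.25*12", the whole enclosed in a FLOOR function that keeps the integer part.

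The same section treats a difference between two dates as a count of days. For a date on or after the first dose, "then study day will be calculated as (date of interest – date of first dose) + 1".

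SAP 7.4 says "Demographics and baseline characteristics will be summarized". Its table has a Subject Age row in the continuous format, with no unit shown, although weight, height and BMI in the same table carry theirs. SAP 11.3 lists the output as Table 14.1.2.1.1, with a companion Baseline Demographics listing, 16.2.4.2.1. No other part of the SAP defines age or converts it back to years.

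**The concern.** The sentence and the label promise years, while the arithmetic delivers months. The rule is an instruction to a programmer, so it matters even though it is one line long. Followed literally, it produces a demographics row whose mean, median and range are impossible for human ages in years. Corrected silently at the programming stage, it leaves the reported ages derived by a rule that the plan does not contain. Age is one of the first items a reader uses to judge who was studied, and with a final sample size of 11 (SAP 4.3) the listing will be read subject by subject.

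**Working it through.** **Inputs**
- Formula as written (SAP 6.6.1): FLOOR((consent date − birth date)/365.25*12), labelled as years.
- Unit of a date difference: days, as in the study-day rule of the same section.
- Software (SAP 6.2): "Analyses and tabulations will generally be prepared using SAS". In SAS, division and multiplication have equal precedence and run left to right.
- Plausible ages: "Male and female subjects ≥18 years old" (Protocol synopsis and 5.2.1, SPR001-naïve subjects), and for the enriched group, "If male, must be 18 to 35 years old, inclusive" (Protocol 5.2.2).
- Day counts: illustrative assumptions, since the documents give no birth or consent dates.

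The SAP gives no worked age, so there is no figure of its own to reproduce.

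**Units.** Days/365.25 = years. Years × 12 = months. FLOOR then gives completed months.

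**Three versions compared**

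| Days | Exact years | As written: FLOOR(days/365.25*12) | Denominator grouped: FLOOR(days/(365.25*12)) | Without the 12: FLOOR(days/365.25) |
|---|---|---|---|---|
| 6,575 | 18.001 | 216 | 1 | 18 |
| 6,935 | 18.987 | 227 | 1 | 18 |
| 10,958 | 30.001 | 360 | 2 | 30 |
| 12,785 | 35.003 | 420 | 2 | 35 |
| 13,133 | 35.956 | 431 | 2 | 35 |
| 18,263 | 50.001 | 600 | 4 | 50 |

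One row in full: 10,958/365.25 = 30.001; 30.001 × 12 = 360.02; the integer part is 360.

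The grouped reading divides by 365.25 × 12 = 4,383 days: 6,575/4,383 = 1.50, integer part 1. It counts 12-year blocks, so neither order of operations yields years.

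**Size of the inflation.** For y completed years and m further completed months (0 to 11), the formula returns 12y + m. The ratio to completed years is therefore 12 + m/y. At y = 18 and m = 11 this is 227/18 = 12.61; at m = 0 it is exactly 12. Evaluated at every day count from just over 18 to just under 80 years, the ratio to completed years runs from 12.00 to 12.61. Against exact, unfloored age it runs from 11.95 to 12.00.

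**Dividing afterwards is not a repair.** 227/12 = 18.92, which is not a completed-years value. The factor has to go before FLOOR is applied.

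**Where the variable goes.** The pre-defined subgroups in SAP 6.4.5 are sex, baseline hormone control and glucocorticoid category; age is not among them. No analysis in SAP sections 8 or 9 uses age. That leaves the demographics table and the listing.

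**The case against.** The best defence is that this is a self-evident slip. The intended unit stands beside the formula, an adult age of 216 would be caught on first review, and nothing inferential depends on the variable. All of that stands as a limit on the consequence. It is not a reason to leave the text alone. SAP section 2 presents the document as the plan fixed in advance and says that substantive modifications will be identified in the study report. Whether or not this one counts as substantive, correcting the rule is cleaner than relying on someone to depart from it.

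A reader might infer two stronger things that the documents do not support.

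The first is that every reported age in this trial is 12 times too large. The documents contain no reported ages, so the error is conditional on literal programming, and the multiple is exactly 12 only when no further month has been completed since the birthday.

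The second is that age-based eligibility checks would fail for everyone. A check with only a lower bound of 18 would pass at 216 or above; only a check with an upper bound, such as 18 to 35, would fail. No check of either kind is planned on this variable. Protocol section 5 has eligibility confirmed from screening evaluations, with the Investigator keeping the screening log. The 18-to-35 limit applies only to SPR001-naïve males, and only if the Sponsor decides to require the enrichment criteria (Protocol 5.2 and 5.2.2). The eligibility listing in SAP 7.5 and the inclusion/exclusion table in SAP 11.3 are not tied to derived age.

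**Conclusion.** The formula is wrong as written: it contradicts its own label, no reading of the operator order gives years, and nothing downstream corrects it. If implemented literally, ages come out 12.0 to about 12.6 times the completed years. That affects one descriptive row and one listing. It changes no endpoint, test, analysis set, eligibility decision or safety conclusion. The correction is worth making because the error is certain and the remedy unambiguous, not because the trial's findings are at risk.

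This rests on two assumptions: that the date difference is in days, as elsewhere in the same section, and that the program follows the SAP text. The second cannot be checked from the documents.

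**What to change.** In SAP 6.6.1, delete the factor 12 inside FLOOR, so that Age (years) = FLOOR((date of informed consent − date of birth)/365.25). On the day counts above this returns 18, 18, 30, 35, 35 and 50, in agreement with the label. Add the unit to the Subject Age row in SAP 7.4, as the rows for weight, height and BMI already do.

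Then confirm that the program behind Table 14.1.2.1.1 and Listing 16.2.4.2.1 computes completed years, with no factor applied before FLOOR and no division by 12 after it. The cost is one deletion in the text, one unit label and a short program check. No new data are needed, and no other analysis has to be rerun.
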